4.3.2 Inclusion Criteria

- Participant is willing and able to give informed consent for participation in the study.
- Female, aged between 25 to 65 years.

• Diagnosed with abnormal cervical cytology by routine screening or having been referred for a clinical indication by the GP/Clinical Practitioner for an abnormal looking cervix or post-coital/inter-menstrual bleeding concerns

4.3.3 Exclusion Criteria

The participant may not enter the study if ANY of the following apply:

- Participant is unable to give consent.
- Pregnant
- HIV/Systemic Immuno-suppression
- Previous contraindication or allergy nail varnish/ nitrocellulose

4.4 Study Procedures

There are no additional visits required for this study.

- 1. During the colposcopy examination, a number of digital images of the cervix will be taken according to standard practice. Images are non-mandatory for the purpose of the research and will not result as a non-compliance if not taken.
- 2. A filter disk (of up to 25mm diameter and marked to indicate the 12 O'clock position) will then be gently pressed onto the surface of the cervix for 10 to 15 seconds prior to it being peeled off and removed for storage. The filter with adherent exfoliated cells will then be fixed (in acetone/methanol, ethanol, or 5% formaldehyde) prior to analysis at the level of cytology or immunostaining or DNA/ RNA analysis as part of the research collaboration between the University of Cambridge and Addenbrookes Hospital.
- 3. In the majority of cases, the remainder of the colposcopy examination will then follow its standard course, without further modification. Colposcopic photographs, if taken, will be compared as well as the colposcopist' view of the cervix.

For a number of cases (10 high grade and 20 low grade) we shall take a conventional cervical screen after the cell lift has been taken. This will be similar in discomfort to a normal cervical screen and add approximately 30 seconds to the overall procedure. This will permit the potential impact of the cell lift procedure on the routine cervical screen to be evaluated. It has already been established that a routine cervical screen disrupts the cell lift procedure. However, it is hypothesised that performing the cell lift procedure before a routine screen will permit both sampling procedures to be performed without issue.

During the final phase of the cell lift project we shall test variations of a prototype device designed to deliver the filter disk to the cervix. In the prototype testing we shall use 10 samples of each prototype and evaluate for purposes of clinician user and patient experience. Subsequently, the prototype will be evaluated against the laboratory process.

The standard operating procedure for use of device follows as:

- Insert a speculum and visualise the cervix.
- Select device (standard for normal or larger speculum; small when using a small speculum). Orientate with fin on handle at 12 o'clock and apply to cervix.
- Maintain light pressure for approximately 15 seconds and then withdraw.
- Avoid agitating the head when in contact with the cervix.
- Remove from vagina and hand to research nurse.
- Research nurse places in formalin fixative for 10-15 seconds and then detaches device head into transport medium.
- The wand is disposed of in clinical waste.

4.4.1 Informed Consent

Informed consent will be taken prior to the examination. The participant will be sent an invitation to take part in the study. When they attend the clinic, the research nurse will discuss the consent and obtain this prior to the participant seeing the colposcopist.

4.4.2 Study Assessments

For the study, we envisage that 800 cell-lifts will be sufficient.

These will be double stained with a pan E4 antibody to identify areas of virus infection (LSIL), along with MCM to identify cells that are progressing through the cell cycle (HSIL). Images of the stained cells will be captured using a digital imaging system prior to H+E staining or staining with the Pap stain. The immunostaining and histology images will be compared against the colposcopy findings and with the results of the biopsy analysis. In some instances, we will request sections from the biopsy material in order to better understand how biomarker expression at the epithelial surface (in the cell-lifts) relates to expression of the same biomarkers in the underlying disease. Once able to define consistently areas where productive infection and high rates of cell turnover is occurring we aim to use P16INK4A (surrogate marker of E7) and P53 (decline of P53 expression as surrogate marker of E6 expression) to further delineate the regions of the lift from high risk or low risk lesions.

As part of the validation of this biomarker approach, we would also like to perform a DNA validation. Here we would like to obtain an additional lift on 10 patients and by performing an insitu localization of DNA we aim to overlay the biomarker map over the DNA map so as to demonstrate co-localisation.

4.5 Definition of End of Study

The end of study is when we have either met our proposed primary objective or if we reach our maximum number of samples.

5. INTERVENTIONS

No interventions beyond those seen in colposcopy

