1. SYNOPSIS

It may be useful to include a synopsis of the study for quick reference. Delete or alter as appropriate/required.

Study Title	Collection of Cervical Cells at Colposcopy using a novel technique for analysis of high risk vs. low risk lesions		
Internal ref. no.	R&D A094381		
Study Design	Observational & Lab Based		
Study Participants	Women referred to colposcopy with abnormal cytology or those requiring a cervical examination		
Planned Sample Size	800 in total		
Follow-up duration	Nil		
Planned Study Period	5 years		
Primary Objective	The aim of the project is to improve the collection and analysis of cells taken from the surface of the cervix in order to identify high risk or low risk cervical cancer precursor lesions		
Secondary Objectives	None		
Primary Endpoint	Demonstrating clear correlation of high/ low risk lesions with novel molecular techniques or achieving 800 samples (whichever is sooner)		
Secondary Endpoints			
Intervention (s)	Removing a layer of cells from the cervix with no trauma and preserving the spatial distribution of cells for analysis		

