6. SAFETY REPORTING (IF APPLICABLE)

6.1 Definition of Serious Adverse Events

Not applicable

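### Section 5 denies any procedure beyond colposcopy and Section 6 sets serious-event reporting aside, yet Section 4.4 adds cell lifts and prototype devices, so harms have no systematic capture

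*Protocol*

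**What the plan says.** Protocol Section 5 consists of one sentence: "No interventions beyond those seen in colposcopy".

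The synopsis, in its intervention row, gives: "Removing a layer of cells from the cervix with no trauma and preserving the spatial distribution of cells for analysis". The same table sets follow-up at nil.

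Section 4.4 describes what is done in the clinic. A filter disk "will then be gently pressed onto the surface of the cervix for 10 to 15 seconds prior to it being peeled off". In the final phase, "we shall test variations of a prototype device designed to deliver the filter disk to the cervix", and for that work "we shall use 10 samples of each prototype and evaluate for purposes of clinician user and patient experience". In 30 cases (10 high grade, 20 low grade) a conventional smear follows the lift. Section 4.4.2 adds a further lift in 10 patients for DNA validation.

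On safety, Section 6.1 (definition of serious adverse events) reads "Not applicable", and Section 6.2 dismisses the reporting procedures in the same way. Section 2 says that participants face no discernible risk, and Section 8 says that applying the template is not thought uncomfortable. Section 4.3.3 nevertheless excludes women with a contraindication or allergy to nail varnish or nitrocellulose.

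**The concern.** Section 5 cannot be read together with the synopsis and Section 4.4. Pressing a membrane onto the cervix to lift cells is the research procedure itself, and a prototype applicator is a research device. Section 8 treats the procedure as additional to standard care, since it says that the visit takes a few minutes longer than usual.

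The contradiction has a practical consequence. A protocol that recognises no study-specific procedure has no reason to collect events from one, and Section 6 follows that line for serious events. Pain, bleeding, a reaction to the membrane or a failure of the detachable device head would then have no defined place in the data, and a serious event would have no route out of the clinic.

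Two things are at stake. One is oversight of participants who undergo procedures done only for research. The other is evidence: the rationale in Section 2 presents the lift as a gentler, non-invasive alternative to scraping, and the plan collects nothing systematic to show this.

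**Working it through.** The protocol gives no safety figure, so there is none to reproduce. The check is a comparison of passages, followed by a short calculation of what event recording could show.

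**Comparison of passages**

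| Procedure | Where described | Within Section 5's wording? | Provision for harms |
|---|---|---|---|
| Filter-disk lift, all participants | Synopsis; 4.4 | No: it is the synopsis intervention | None |
| Second lift, 10 patients | 4.4.2 | No | None |
| Prototype device, 10 samples each | 4.4 | No | Patient and user experience, no measure named |
| Smear after the lift, 30 cases | 4.4 | Arguably yes | None; discomfort acknowledged ("This will be similar in discomfort to a normal cervical screen") |

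Section 6 concerns serious events only. No other section defines, collects or routes events of any severity. Section 8.1 mentions a CRF, but its fields are not shown.

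**What recording could show**

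Inputs:
- Planned total: 800 (synopsis; Section 7.1).
- Already recruited in the first year: 105 (Section 7.1).
- Samples per prototype: 10 (Section 4.4).

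Recording introduced by amendment can cover only later participants. Assuming one lift each, at most 800 − 105 = 695 lifts remain. The number is smaller if recruitment has gone on since that count, or if the study stops before 800, as Sections 4.2 and 4.5 allow.

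With zero events in n lifts, the upper end of the two-sided exact 95% interval is 1 − 0.025^(1/n):
- n = 695: 1 − 0.025^(1/695) = 0.0053, about 0.53%.
- n = 10: 1 − 0.025^(1/10) = 0.308, about 30.8%.

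The chance of seeing at least one event in 10 uses is 1 − (1 − p)^10. The protocol gives no event rate, so p is assumed over a range:
- p = 1%: 9.6%.
- p = 5%: 40.1%.
- p = 10%: 65.1%.

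Even a harm affecting one use in ten would therefore go unseen for a given prototype about 35% of the time (100% − 65.1%). If nothing is recorded, none of these limits can be calculated.

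**The case against.** The strongest reply is that the risk is low, that the lift technique was piloted and used in the first year, and that the study makes no safety inference. The absence of trauma is a description in the synopsis, not an objective or endpoint, and no estimate of sensitivity, specificity, PPV or NPV changes. That is correct, and it limits the weight of the point. It does not remove the contradiction or supply a reporting route.

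A reader might also infer more than the documents support:

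- **That Section 5 denies any intervention.** It denies only those beyond colposcopy. A conventional smear arguably falls inside that wording, so the 30 added smears are weak evidence of contradiction. The lifts and the prototype devices carry the point.
- **That Section 6 switches off all safety reporting.** It speaks only of serious events. On non-serious events and device failures the protocol is silent, which is different from a rule against recording them.
- **That harms would go wholly unrecorded.** Patient and clinician experience is to be evaluated for the prototypes, and discomfort or handling problems could surface there. No instrument or harm measure is named, however, and the other lifts are not covered.
- **That the prototypes are untried and meet their first human use here.** The protocol does not say whether they were used before.
- **That the full 800 lifts could bound the risk, at 0.46% for zero events.** The 105 patients already recruited put that out of reach for recording that starts now.

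**Conclusion.** The point holds in bounded form. Section 5 is inconsistent with the synopsis and with Sections 4.4 and 4.4.2. Section 6 sets serious-event definition and reporting aside, and nothing elsewhere provides for lesser events or device failures. As written, harms are not systematically captured, and the statements about trauma and risk will rest on assertion. This is protocol content that the document addresses and fixes badly, so it is not detail left to an analysis plan.

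On size, complete recording on at most 695 remaining lifts with no events would bound the risk at about 0.53% (two-sided exact 95%). Ten uses of one prototype would bound it only at about 30.8%, so no trauma-free statement can be made for a single prototype on that number. The 0.53% assumes one lift per remaining participant, recording that starts straight after the 105, recruitment up to 800, and pooling of disk and prototype lifts. With follow-up at nil, both limits concern only events seen at the visit and say nothing about delayed harm. The change is worth making, but it does not threaten the diagnostic accuracy analysis.

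**What to change.** 1. Reconcile Section 5 with the synopsis and Sections 4.4 and 4.4.2 by listing the study-specific procedures: the filter-disk lift, the additional lift in 10 patients and the prototype devices. State whether the smear after the lift counts as one of them.
2. Replace the entries in Sections 6.1 and 6.2 with recording of immediate adverse events and device failures on the CRF at each remaining lift, including an explicit entry when none occurred, and with a definition and reporting route for serious events.
3. Tabulate counts by sampling method (disk, and each prototype separately). If the pooled figure is quoted, give its exact interval and say that it covers events at the visit only.
4. Until such data exist, word the statements on trauma, risk and discomfort as expectations. Make no trauma-free statement for a prototype on 10 uses.

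The cost is a protocol amendment, a CRF change and a small amount of time for the research nurse, who already receives the device at the examination. Defining serious events and setting up their reporting route takes somewhat more work than the CRF entry. No extra visits or participants are needed.

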6. SAFETY REPORTING (IF APPLICABLE)

6.1 Definition of Serious Adverse Events

Not applicable

6.2 Reporting Procedures for Serious Adverse Events

Not relevant

7. STATISITICS

7.1 The Number of Participants

For the study, we envisage that 800 cell-lifts will be sufficient (with the majority being smear abnormal patients and approximately 50 patients being referred for clinical indications). Though this number has not been formulated by a formal power calculation, we envisage that this would certainly be an adequate number so as to get over certain hurdles such as obtaining a monolayer of cells on the membrane, staining with low level of background noise and demonstrating lesions.

During the first year of study we have recruited 105 patients. The majority of these patient samples have been used to create a standardized, reproducible protocol. This protocol has then been tested on 31 patients successfully with a corresponding sensitivity of 87% and positive-predictive value of 87%. We have now commenced a collaboration with [name] who has calculated that a sample size of 800 patients would give us a robust analysis of the true sensitivity, specificity, PPV and NPV of our diagnostic approach with narrow confidence intervals. As we have already recruited 105 patients, we would like to therefore increase the total number of patient during the study time to 800 in total. To effectively do this we would also require an increase in the duration of the study period to the end of April 2022. The end of April is referring to end of study recruitment and the sample analysis will be completed within a year after the recruitment is closed.

7.2 Analysis of Endpoints

An analytical plan will be developed by the Translational Lead, [name]. This will include triple staining and analysis of collected samples, against sensitivity, specificity, PPV/NPV corrected for population prevalence.

8. ETHICS

The procedure will take a few minutes longer than the standard procedure and this will fall within the normal range of times for this type of clinical investigation. The application of the template is not felt to cause discomfort.

The study has been reviewed and approved by the South Central – Oxford B Research Ethics Committee.

8.1 Participant Confidentiality

The study staff will ensure that the participants' anonymity is maintained. The participants will be identified only by date of birth and a participants ID number on the CRF and any electronic database and where required on sample labels. All documents will be stored securely and only accessible by study staff and authorised personnel. The study will comply with the General Data Protection Regulation (GDPR) 2018, which requires data to be anonymised as soon as it is practical to do so.

8.2 Other Ethical Considerations

Only participants able to understand the study will be involved

9. DATA HANDLING AND RECORD KEEPING

All study data will be entered on an MS Excel spreadsheet by the research nurse. The participants will be identified by a study specific participants number and/or code in any database. The name and any other identifying detail will NOT be included in any study data electronic file.

10. FINANCING AND INSURANCE

Finance:

The cost of staining and handling of the templates will be borne by the programme grant and CRUK Early Detection Award, from [name] (University of Cambridge). Incidental expenses required at Addenbrookes will be borne by ACT (Gynaecological Cancer Fund). Research Costs incurred by Addenbrookes, including Trial Management and Research Nurse time, will be covered by the CRUK Early Detection Award.

Insurance: Cambridge University Hospitals NHS Foundation Trust

